11.3 Data Analyses Plans

PFS will be defined as the time from random assignment to disease progression or death from any cause, whichever comes first. OS will be defined as the time from random assignment to death from any cause; living patients will be censored at the date of last follow-up. Survival will be estimated and plotted by the Kaplan–Meier method. In addition, the median progression-free and overall survival times will be reported along with the 95% confidence intervals. The cox proportional hazards regression model will be used to obtain hazard ratios (HRs) and the log-rank test will be utilized to compare survival estimates between the maintenance group and the control observation group. Secondary endpoints will be analyzed when the required number of events for the primary endpoint (PFS) has been met. The DCR is defined as the proportion of patients with a best overall response of CR, PR, or SD. The ORR is defined as the proportion of patients with a best overall response of CR or PR. All randomized subjects will consist of the safety population. This population will be used for all summaries of safety data (AEs, concomitant medications, laboratory data). P-values less than 0.05 will be considered significant. All statistical analyses will be performed using SAS (Version 9.4; SAS Institute, Cary, NC). [name] will serve as the study statistician.

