5.7 Duration of Follow-Up

Patients will be followed either with clinic visits or phone interviews yearly for two years. Patients removed from treatment for unacceptable adverse event(s) will be followed clinically until resolution or stabilization of the adverse event, and then via clinic visits or phone interviews yearly for two years.

The following information will be collected:

- Date of follow up
- Is patient dead or alive?
- If dead, document exact date of death.
- Further treatment(s), if any
- Document date of disease progression

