11.2 Sample Size and Accrual

ES-SCLC (i.e. SCLC that has spread beyond the supraclavicular areas or with distant metastases) remains incurable with current management options, and patients are treated with combination chemotherapy. Several chemotherapy combinations are active in SCLC, but usually a platinum-containing regimen is chosen. The ORR of platinum-based therapy administered to patients with ES-SCLC ranges from 40 to 80%, and the median PFS ranges from 5 to 7 months in patient series treated in a clinical trial setting (phase-II/III studies) [9, 10, 48-55]. A placebo-controlled randomized phase II study of maintenance sunitinib shows that median PFS was 2.1 months in the placebo group[56].

Based on historic average clinical outcomes, we propose a clinical study that will be integrated by a dose finding approach followed by a randomized phase II study with PFS as the primary endpoint, designed to have 80% power for a two-sided 0.05 level test. The completion of the first part of the study will require approximately 8-9 months for accrual assuming 9 to 12 patients will be required for the completion of the phase I portion with the participation of 7 institutions (Georgetown Lombardi comprehensive Cancer Center, Memorial Sloan Kettering Cancer Center, University of California, Los Angeles, University of California, San Francisco, Vanderbilt University, Hackensack University Medical Center, and Walter Reed National Military Medical Center).

For the phase II portion, assuming a median PFS of 2 months following completion of first-line therapy with a platinum-based chemotherapy for ES-SCLC in the control arm, and an expected median PFS of 5 months for the maintenance therapy with $^{177}\text{Lu-DOTA}^0\text{-Tyr}^3\text{-Octreotate}$ and nivolumab in the experimental arm (hazard ratio 0.4), it will be required to document 40 PFS events from a total population of 44 patients enrolled during a period of 18 month, including a minimum follow up of 10 months, with an expected accrual rate of 3-4 patients per month and the participation of 6-7 institutions. Assuming a potential 15% dropout, the total number of patients to recruit will be 52 [57-59].

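### OS is tested at the 40-event PFS trigger, and no later OS analysis is planned although deaths are collected for two years

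*Combined protocol and SAP*

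**What the plan says.** Section 11.3 sets one time point for all secondary endpoints: "Secondary endpoints will be analyzed when the required number of events for the primary endpoint (PFS) has been met". The number comes from section 11.2: "it will be required to document 40 PFS events from a total population of 44 patients".

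OS is a secondary objective (section 3.3.2). Section 11.3 defines it from randomisation, compares survival between arms by log-rank test and Cox model, and calls P-values below 0.05 significant. I read that as covering OS as well as PFS, since the same paragraph reports medians for both.

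Section 5.7 states: "Patients will be followed either with clinic visits or phone interviews yearly for two years". Sections 5.7 and 6.3 list vital status and exact date of death among the items collected, and the study calendar repeats the annual contact. Section 11.3 gives no OS cut-off date, death target or final OS analysis.

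Section 11.2 also describes the patients as "enrolled during a period of 18 month, including a minimum follow up of 10 months". Section 11.3 does not say whether the 40-event analysis must wait for that minimum.

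**The concern.** A trigger set by PFS events is natural for PFS. In this disease progression comes well before death for many patients, so the same trigger catches OS early. If the rule is followed as written, the only planned significance test of OS uses the less mature data, and the deaths recorded afterwards have no planned analysis.

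The trial is open-label. If a later OS analysis is done anyway, its cut-off will be chosen after the first OS result is known, which weakens it. Post-treatment contact is yearly and living patients are censored at last follow-up, so vital status at an event-driven cut-off could also be up to a year out of date.

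**Working it through.** **Inputs from section 11.2.** "designed to have 80% power for a two-sided 0.05 level test"; "assuming a median PFS of 2 months following completion of first-line therapy"; "an expected median PFS of 5 months for the maintenance therapy" (hazard ratio 0.4); 40 events from 44 patients; 15% dropout, giving 52; "with an expected accrual rate of 3-4 patients per month". Imaging is every 8 weeks (section 6.2).

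**Assumptions.** Allocation 1:1 (no ratio is stated); uniform accrual; exponential times; median OS of 6, 9 or 12 months from randomisation, the same in both arms. For orientation only, section 2.1.2 cites about 10 months for first-line ES-SCLC and 5.4 months for relapsed disease; neither is measured from this trial's randomisation. The two-year point is taken as 24 months after the last patient is randomised.

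**1. Reproduce the plan.** Events = 4(1.96 + 0.84)² / (ln 0.4)² = 37.4, so 38; with 40 events power is 82.6%. Recruitment: 44 / 0.85 = 51.8, so 52.

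Expected events per arm at month T with accrual over A months: (N/2) × [1 − (e^(−λ(T−A)) − e^(−λT)) / (λA)], where λ = ln 2 / median. With N = 44, A = 8, T = 18:
- control (median 2): 22 × (1 − 0.0106) = 21.8
- experimental (median 5): 22 × (1 − 0.1511) = 18.7
- total 40.4

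So 40 events, 44 patients, 18 months and 10 months' follow-up fit together if accrual takes 8 months. That needs 44/8 = 5.5 patients per month (52/8 = 6.5 for the full number), against the stated 3–4. At 3–4 per month, 52 patients take 52/4 = 13 to 52/3 = 17.3 months.

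**2. When event 40 falls, and how many have died.** Simulated, with each PFS event dated to the next 8-week scan. PFS already includes death, so no deaths are added to the 2- and 5-month medians. Deaths are a percentage of all randomised; each range runs from OS median 12 down to 6 months.

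| Case | Event 40, months after last patient in | Dead at event 40 | Dead two years after last patient in |
|---|---|---|---|
| 52 patients, 3–4/month, no dropout | 1.6–2.8 | 40–64% | 82–97% |
| Same, 15% (8 patients) contribute no event | about 7–8 | 55–79% | 82–97% |
| 44 patients accrued in 8 months | about 9–10 | 53–77% | 80–96% |

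The last column uses the formula in step 1. For example, with A = 13, T = 37 and OS median 12, 1 − (0.250 − 0.118)/0.751 = 82%. Without the scan delay, the first case gives 0.8–2.0 months and 37–61% dead.

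**3. If the 10-month minimum also applies.** For 52 patients at 3–4 per month the cut-off is month 23–27.3, and the formula gives 61–86% dead.

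**4. Precision.** The 95% CI for the OS hazard ratio extends by a factor exp(1.96 × 2/√deaths) each way. For 52 patients:
- no dropout: 40–64% is 21–33 deaths, factor 2.35–1.98
- 15% contributing no event: 55–79% is about 28–41 deaths, factor 2.10–1.84
- two years: 82–97% is 43–50 deaths, factor 1.82–1.74

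Power for an OS hazard ratio of 0.6 (illustrative) is about 21–31% at 21–33 deaths and 39–44% at 43–50. These figures assume nobody is lost to survival follow-up.

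**The case against.** **OS is secondary and confounded.** Section 5.1.2 allows cross-over at progression precisely because PFS, not OS, is primary, and no power is claimed for OS. This stands as a limit on what any OS result can show. It does not justify placing the only OS test at 0.05 at the PFS trigger.

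**Nothing forbids a later analysis.** True, and the follow-up has another use: section 6.3 also collects long-term myelosuppression, myelodysplasia and secondary malignancies. It would be wrong to infer that the survival data are barred from analysis. The gap is that no analysis is specified.

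**The 10-month minimum may govern.** Sections 11.2 and 11.3 can be read together as 40 events and at least 10 months' follow-up. OS is then more mature, but still short of the two-year figures (61–86% against 82–97% for 52 patients).

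**Stronger readings to avoid.** A reader might infer that OS is analysed about when accrual ends, with the last patients hardly followed. That comes close only if all 52 patients are followed without dropout; section 11.2 itself allows 15%. Adding separate deaths to the PFS medians would bring the trigger earlier still, but it counts deaths twice, because section 7.1.6 defines PFS as progression or death.

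A reader might also infer that ORR and DCR are compromised by patients without a first scan. About 0–2 of 52 patients would have under 8 weeks' follow-up without dropout, and almost none with it. Section 7.1.1 also limits response evaluability to re-evaluated patients or early progressors. The documents do not support that claim.

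**Conclusion.** The point holds for OS only. As written, OS is tested once, at 40 PFS events, and two years of survival data have no planned comparison. Across the three cases in the table, roughly 18 to 42 percentage points of the patients would die between that test and two years after the last patient is randomised. The loss is smaller if dropout is as planned or the 10-month minimum is honoured, but it does not vanish.

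The percentages depend on an OS median of 6–12 months, which is my assumption. The direction does not: a cut-off at event 40 precedes the two-year point in every case. The gain is better precision and a pre-specified cut-off. It does not make the trial adequately powered for OS. This should be corrected, but it does not affect the primary analysis.

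**What to change.** In section 11.3:

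- Keep 40 events as the trigger for PFS, and state whether that analysis also waits for the 10-month minimum follow-up in section 11.2. The 18-month period and the 3–4 per month accrual rate should be reconciled at the same time.
- Label any OS result at that trigger as descriptive.
- Make the OS log-rank and Cox comparison the analysis done when all patients have died or completed the two-year follow-up, and state when those two years start.
- Require a vital-status update for all patients at each cut-off.

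The cost is a few sentences, a round of survival contacts, and one later analysis of data already being collected. The final OS result is reported later, and cross-over will still limit its interpretation.

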7.1.1 Definitions

Evaluable for toxicity: All patients will be evaluable for toxicity from the time of their first treatment with $^{177}\text{Lu-DOTA}^0\text{-Tyr}^3\text{-Octreotate}$ and nivolumab.

Evaluable for objective response: Only those patients who have received at least one cycle of therapy, and have had their disease re-evaluated will be considered evaluable for response. These patients will have their response classified according to the definitions stated below. (Note: Patients who exhibit objective disease progression prior to the end of cycle 1 will also be considered evaluable.)

Evaluable Non-Target Disease Response: Patients who have lesions present at baseline that are evaluable but do not meet the definitions of measurable disease, have received at least one cycle of therapy, and have had their disease reevaluated will be considered evaluable for non-target disease. The response assessment is based on the presence, absence, or unequivocal progression of the lesions.

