7.1.4.3 Evaluation of Best Overall Response

The best overall response is the best response recorded from the start of the treatment until disease progression/recurrence (taking as reference for progressive disease the smallest measurements recorded since the treatment started). The patient's best response assignment will depend on the achievement of both measurement and confirmation criteria.

Table 7. Evaluation of patients with measureable disease.

Target Lesions	Non-Target Lesions	New Lesions*	Overall Response
CR	CR	No	CR
CR	Non-CR/Non-PD	No	PR
CR	Not evaluated	No	PR
PR	Non-CR/Non-PD/not evaluated	No	PR
SD	Non-CR/Non-PD/not evaluated	No	SD
PD	Any	Yes or No	PD
Any	PD**	Yes or No	PD
Any	Any	Yes	PD

* See RECIST 1.1 manuscript for further details on what is evidence of a new lesion.

****** In exceptional circumstances, unequivocal progression in non-target lesions may be accepted as disease progression.

Note: Patients with a global deterioration of health status requiring discontinuation of treatment without objective evidence of disease progression at that time should be reported as “symptomatic deterioration”. Every effort should be made to document the objective progression even after discontinuation of treatment.

Table 8. Evaluation of patients with non-measurable disease

Non-Target Lesions	New Lesions	Overall Response
CR	No	CR
Non-CR/non-PD	No	Non-CR/non-PD*
Not all evaluated	No	Not evaluated
Unequivocal PD	Yes or No	PD
Any	Yes	PD
* ‘Non-CR/non-PD’ is preferred over ‘stable disease’ for non-target disease since SD is increasingly used as an endpoint for assessment of efficacy in some trials so to assign this category when no lesions can be measured is not advised.		

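### DCR as defined in 11.3 scores non-progressing patients with only non-measurable disease as failures, and 11.3 does not say which patients form the denominator for DCR or ORR

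*Combined protocol and SAP*

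**What the plan says.** All references are to the combined protocol and SAP.

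- **11.3, rates.** On disease control: "The DCR is defined as the proportion of patients with a best overall response of CR, PR, or SD". ORR is defined in the same way from CR and PR. Neither definition names an analysis set. The only population named in 11.3 is all randomized subjects, and that is for safety summaries.
- **3.3.2, scope.** DCR and ORR are phase II secondary objectives, assessed after treatment with the combination.
- **7.1.4.3, Table 8.** Patients with non-measurable disease can be CR, Non-CR/non-PD, not evaluated or PD. There is no SD row and no PR row. On SD, the footnote says "so to assign this category when no lesions can be measured is not advised".
- **7.1.1, response-evaluable set.** The main definition reads: "Only those patients who have received at least one cycle of therapy, and have had their disease re-evaluated will be considered evaluable for response". It continues: "These patients will have their response classified according to the definitions stated below". One exception is given: "Patients who exhibit objective disease progression prior to the end of cycle 1 will also be considered evaluable".
- **7.1.1, non-target disease.** A separate entry covers "Patients who have lesions present at baseline that are evaluable but do not meet the definitions of measurable disease". Such patients who have had a cycle of therapy and "have had their disease reevaluated will be considered evaluable for non-target disease".
- **Note to Table 7.** It foresees patients whose health declines, "requiring discontinuation of treatment without objective evidence of disease progression at that time".
- **4.2.** Neither the inclusion nor the exclusion criteria for phase II require measurable disease.

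**The concern.** **Numerator.** A patient whose non-measurable lesions persist without progressing has a defined category in Table 8, but 11.3 does not list that category as disease control. Such patients are foreseeable. Phase II enrols patients who responded or were stable after first-line chemotherapy (5.1.2). Baseline is measured no more than 28 days before treatment (7.1.3), so after any shrinkage. Section 7.1.2 classes small lesions, bone lesions and effusions as non-measurable.

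**Denominator.** Section 11.3 neither names a set nor refers to 7.1.1. If the 7.1.1 definition is used, a combination-arm patient who dies or stops before re-evaluation, without documented progression, leaves the denominator. Such patients are unlikely to be disease-control successes, so removing them raises both rates.

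The two gaps push DCR in opposite directions, so one set of patients can yield different rates. The trial is open-label, and the reading is best fixed before data are seen.

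**Working it through.** **Plan's own figures.** None is stated for DCR or ORR. The only relevant figure is the phase II size in 11.2: 44 / (1 − 0.15) = 51.8, rounded up to 52, which reproduces the plan. The allocation ratio is not stated. Assuming 1:1, the combination arm has 52 / 2 = 26 patients.

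**Direction of each effect.** The true control rate D, the share q with only non-measurable disease and the share e not evaluable are not in the documents. Assume D = 60%.

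- Numerator gap, with no CRs among the non-measurable-only patients and the same control rate in them: DCR reads D × (1 − q). For q = 10%, 20%, 30% this is 54%, 48%, 42%.
- Evaluable-only denominator, with none of the dropped patients controlled: DCR reads D / (1 − e). For e = 5%, 10%, 15% this is 63%, 67%, 71%.

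**Both together, in one assumed arm of 26.** Five patients have only non-measurable disease: 3 are controlled, none by CR, and all are re-evaluated. Twenty-one have measurable disease: 13 are controlled, of whom 4 are responders, and 2 of the other 8 stop early without documented progression. The evaluable set is 26 − 2 = 24.

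| Reading | DCR | ORR |
|---|---|---|
| 11.3 numerator, all 26 | 13/26 = 50% | 4/26 = 15% |
| 11.3 numerator, evaluable 24 | 13/24 = 54% | 4/24 = 17% |
| Non-CR/non-PD counted, evaluable 24 | 16/24 = 67% | 4/24 = 17% |
| Non-CR/non-PD counted, all 26 (proposed) | 16/26 = 62% | 4/26 = 15% |

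Over all 26, the numerator gap lowers DCR by 3/26 = 12 points. Dropping the two early stops raises DCR by 4 to 5 points and ORR by about 1 point.

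**Are early failures plausible?** The first scan is at cycle 2 day 1, after 56 days (1.84 months). With the 5-month median PFS that 11.2 expects for the combination, and assuming exponential PFS, 1 − 0.5^(1.84/5) = 22.5% progress or die by then, about 6 of 26. How many would lack documented progression cannot be derived from the documents; the 2 used above is an assumption.

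**The case against.** **The protocol does have a response set.** Section 7.1.1 says who is evaluable and links those patients to the response definitions. It would be wrong to infer that the protocol contains no denominator at all. That stands: the gap is that 11.3 does not adopt a set. Adopting 7.1.1 would settle the ambiguity, but not the upward bias from early deaths and stops.

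**Non-measurable patients are not clearly lost from DCR.** A reader might infer from the separate non-target entry in 7.1.1 that these patients form their own set and drop out of DCR. In the example that would give 13/21 = 62% or 13/19 = 68%, and an ORR of 4/19 = 21%. The text does not support this. The objective-response definition asks only for a cycle and re-evaluation, not for measurable disease, so these patients meet it. The plain readings are 50% and 54%.

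**The Table 8 footnote was deliberate.** It withholds the SD label because SD is used as an efficacy endpoint, and leaving these patients out of an efficacy numerator could be called consistent with that. But the footnote concerns which label to use. It does not say that a patient without progression is a disease-control failure. Separate tabulation respects it.

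**All randomized is not the set in the objective.** Section 3.3.2 speaks of assessment after treatment, and an all-randomized set may include patients never dosed. That is a fair point about the choice of estimand. All randomized is the conservative choice.

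**The inputs are assumed.** That stands in full. The documents give neither the non-measurable share nor the control rate.

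**Conclusion.** The concern holds on two counts. As 11.3 is written, non-progressing patients with only non-measurable disease who are not in CR count against DCR, so it is understated. If the silence on denominator is filled from 7.1.1, patients who die or stop early without documented progression are dropped, and both rates are overstated.

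Under the assumed inputs, DCR as written is 50% or 54%, against 62% under a rule that settles both points; ORR differs only between 17% and 15%. These sizes rest on 1:1 allocation and on invented counts for non-measurable disease, control, response and early stops. They show direction and possible scale and do not predict this trial.

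Severity is minor. A reader might infer that the main comparison is compromised, but primary PFS and the sample size do not use these definitions, and no test of DCR or ORR is promised. Nor do the documents suggest any intention to choose a reading after the data are seen.

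**What to change.** Add two sentences to 11.3:

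1. Non-CR/non-PD counts as disease control in DCR and is tabulated separately from SD.
2. The denominator for DCR and ORR is all patients randomized to the combination arm, and patients not re-evaluated count as failures. Evaluable-only rates and an ORR limited to patients with measurable disease are supplementary.

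Because 3.3.2 ties these rates to the combination, no rule for the observation arm is needed.

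**Cost.** No new data or scans. The rates will be somewhat less favourable than evaluable-only rates. ORR is also diluted, because Table 8 has no PR row and non-measurable-only patients can respond only through CR. In the example, 4/21 = 19.0% among all measurable patients becomes 4/26 = 15.4% when the five non-measurable-only patients are added, a fall of 3.7 points. The supplementary measurable-disease ORR makes that dilution visible.

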3.3 Secondary objectives

- 3.3.1** To characterize the safety profile of $^{177}\text{Lu-DOTA}^0\text{-Tyr}^3\text{-Octreotate}$ in combination with nivolumab. [Applicable to both phase 1 and 2 portions]
- 3.3.2** In patients who were not progressing before initiating combo therapy: [Applicable to the phase 2 portion]
- To assess DCR and ORR after treatment with $^{177}\text{Lu-DOTA}^0\text{-Tyr}^3\text{-Octreotate}$ plus nivolumab.
 - To assess OS
 - To assess whether the metabolic response seen on a NETSPOT[®] PET scan obtained on cycle 2 day 1 will predict response to study treatment.

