5.0 TREATMENT PLAN

5.1 Treatment Dosage and Administration

5.1.1 Phase I

5.1.1.1 Dose Limiting Toxicity (DLT)

A DLT is defined as any toxicity not attributable to the disease or disease-related processes under investigation, which occurs from the first dose of study treatment (Day 1, Cycle 1) up to the last day of the cycle (Day 57). To be considered as DLT, it must be related to the study drugs (attributions: possible, probable, and definite) while fulfilling one of the following criteria as per the NCI Common Toxicity Criteria for Adverse Events (CTCAE) version 4.03:

- Toxicity grade 2 for platelets and any other grade 3 or 4 toxicity, excluding
 - Grade 3 diarrhea, nausea, or vomiting if it can be controlled with supportive therapy
 - Grade 3 endocrinopathy that is managed with or without systemic corticosteroid therapy and/or hormone replacement therapy and the patient is asymptomatic.
- Persistent (>21 days) non-hematologic grade 2 adverse events despite optimal medical management and treatment delay > 21 days
- Any other toxicity:
 - if worse than baseline value, documented, clinically relevant and/or unacceptable, and is judged to be a DLT by the investigators
 - if results in a protocol defined stopping criteria
 - if results in disruption of dosing schedule

Patients experiencing DLT will be monitored weekly until toxicity stabilization, and then every two weeks until normalization.

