5.1.1.2 Dose Escalation and Treatment Duration

Treatment will be administered on an outpatient basis.

A standard dose-escalation phase I design will be used. Three subjects will be enrolled at each

dose level in the absence of DLT. Please find the details in the dose escalation table below.

Dose escalation table

Number of Patients with DLT at a Given Dose Level	Escalation Decision Rule
0 out of 3	Enter 3 patients at the next dose level.
≥ 2	Dose escalation will be stopped. This dose level will be declared the maximally administered dose (highest dose administered). Three additional patients will be entered at the next lowest dose level if only 3 patients were treated previously at that dose.
1 out of 3	Enter at least 3 more patients at this dose level. 
 • If 0 of these 3 patients experience DLT, proceed to the next dose level. • If 1 or more of this group suffer DLT, then dose escalation is stopped, and this dose is declared the maximally administered dose. • Three additional patients will be entered at the next lowest dose level if only 3 patients were treated previously at that dose.
≤ 2 out of 6 at highest DL	This is generally the recommended phase 2 dose. At least 6 patients must be treated at the recommended phase 2 dose.

Selection of the starting dose of $^{177}\text{Lu-DOTA}^0\text{-Tyr}^3\text{-Octreotate}$ and nivolumab is based on the results from previous clinical studies with each compound used as single agent and the fact that the combination has not been tested in clinical trials. The first dose of $^{177}\text{Lu-DOTA}^0\text{-Tyr}^3\text{-Octreotate}$ will be given two weeks after the first administration of nivolumab. Studies have shown that intravenous administration of amino acids has a renal protective effect [46]. An infusion of amino acids will be started 30 minutes before the administration of $^{177}\text{Lu-DOTA}^0\text{-Tyr}^3\text{-Octreotate}$ and last 4 hours (Table 3).

Patient Replacement

Three patients within a dose level must be observed for one cycle (56 days) before accrual to the next higher dose level may begin. If a patient is withdrawn from the study prior to completing 56 days of therapy without experiencing a DLT prior to withdrawal, an additional patient may be added to that dose level.

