After the dose finding of the phase 1 portion is concluded, the phase 2 will start. The major end of the phase I is the safety and tolerability. Activity will not be adequately assessed in the phase I portion. The total number of patients required for the whole study will be 61-64 (phase I: 9-12 patients, phase II: 52 patients).

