Amylase	X										
Lipase	X										
HBsAg ^e	X										
anti-HCV ^e	X										
anti-HIV ^e	X										
Pregnancy test ^f	X		X ^f				X ^f				
Tumor biopsy	X ^g	Optional at the time of progression									
Nivolumab ^h		X	X	X	X	X	X	X	X		
¹⁷⁷ Lu-DOTA ⁰ -Tyr ³ -Octreotate			X				X ^h				
Long-term follow up including survival											X ⁱ

- a: Initial tumor assessment will be performed at C2 D1 (\pm 7 days) and every 8 weeks (\pm 7 days) thereafter.
 - b: Refer to section 6.1 for details
 - c: On treatment Netspot only on cycle 2 day 1 (\pm 3 days)
 - d: Thyroid function testing will be done every cycle on day 1 (\pm 3 days) and day 29 (\pm 3 days). Does not need to repeat on C1D1.
 - e: Within three months prior to starting study treatment
 - f: Only for women of child bearing potential (WOCBP). Within 24 hours prior to the administration of $^{177}\text{Lu-DOTA}^0\text{-Tyr}^3\text{-Octreotate}$.
 - g: Optional. Utilization of archival tissue will be allowed.
 - h: May be given one day earlier or delayed up to 1 week. $^{177}\text{Lu-DOTA}^0\text{-Tyr}^3\text{-Octreotate}$ will only be given for 4 cycles.
 - i: Annually for two years
 - j: C1D1 laboratory tests do not need to be repeated if the screening laboratory tests were done within 7 days from C1D1.
- * Refer to section 6.2 for details about time windows within which each procedure should be performed.

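### As worded, the Section 11.3 safety population omits all phase I patients and counts never-dosed ones; the nonserious AE window and the pre-treatment SAE rule also differ between sections

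*Combined protocol and SAP*

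**What the plan says.** **Analysis set.** Section 11.3: "All randomized subjects will consist of the safety population". It continues: "This population will be used for all summaries of safety data (AEs, concomitant medications, laboratory data"). Section 5.1.1.2 describes phase I as cohort dose escalation. Randomization appears only in phase II (5.1.2, 11.1).

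**Scope of the safety aim.** Safety objective 3.3.1 is marked "Applicable to both phase 1 and 2 portions". Section 11.2 adds "The major end of the phase I is the safety and tolerability" and gives the planned sizes as "phase I: 9-12 patients, phase II: 52 patients".

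**Who is evaluable for toxicity.** Sections 5.3.1 and 7.1.1 both rest this on receiving treatment, with no restriction by phase.

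**Nonserious AEs.** Section 8.1.1 reports AEs to 30 days after the last dose. Section 8.3 uses the same 30 days, counted from the last dose or last observation visit, but stops earlier if new systemic anti-cancer therapy begins. Appendix E, which 8.3.3.2 makes mandatory, asks for at least 100 days after the last dose.

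**SAEs before treatment.** Section 8.3 limits these to events caused by a protocol-mandated intervention. Appendix E collects every SAE from consent, related or not.

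**Visits after treatment.** Section 6.2 has one visit at 30 (± 7) days from treatment termination, if the patient is available. Section 6.3 and Appendix D then give yearly contact for two years.

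**The concern.** The safety tables are the main product of phase I, and 5.1.1.2 says that the combination has not been tested in clinical trials. A programmer who follows 11.3 to the letter would produce AE, concomitant medication and laboratory tables with no phase I patient in them, and so no display by phase I dose level. The same tables would count a combination-arm patient who was randomized but never dosed. That patient adds to the denominator without being at risk from the drugs, which dilutes the AE rates.

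The two collection conflicts matter for a different reason. An analysis set can be redefined at any time before the tables are run. An event that no one asked about during follow-up may not be recoverable.

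**Working it through.** **1. The plan's own counts.** 44 / (1 - 0.15) = 51.8, rounded up to 52 for phase II, as stated in 11.2. Adding phase I: 9 + 52 = 61 and 12 + 52 = 64, which reproduces the stated total of 61-64.

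**2. Effect of the 11.3 wording.** Randomized patients: 52. Phase I patients in the set: 0. Share of planned patients left out: 9/61 = 14.8% to 12/64 = 18.8%.

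**3. The three statements on who counts for safety.**

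| Source | Who counts | Phase I patients | Randomized to combination, never dosed |
|---|---|---|---|
| 11.3 | Randomized | Out | In |
| 5.3.1 and 7.1.1 | Treated | In | Out |
| Objective 3.3.1 | Both phases | In | Not addressed |

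Section 5.1.2 allows up to 2 weeks between randomization and the start of treatment for patients without radiotherapy after chemotherapy, so never-dosed patients can occur. The documents give no rate, and none is assumed here.

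**4. Nonserious AE windows.** Appendix E sets a minimum of 100 days, against 30 days in 8.1.1 and 8.3. The difference is therefore at least 100 - 30 = 70 days. It is larger under 8.3 when new systemic therapy starts before day 30.

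**5. Can the visit schedule serve the longer window?** The post-treatment visit falls on day 23 to 37 (30 ± 7). Assuming that treatment termination is the day of the last dose, the days up to day 100 with no scheduled contact number 100 - 37 = 63 to 100 - 23 = 77. The yearly contact in 6.3 does ask about long-term myelosuppression, myelodysplasia and secondary malignancies. Patients removed for unacceptable AEs are followed until resolution or stabilization, but that covers events already known. Any other new nonserious AE in this interval has no scheduled capture.

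**6. Pre-treatment SAEs.** An unrelated SAE after consent and before the first dose is not requested by 8.3 and is requested by Appendix E. A site cannot tell from the protocol which rule applies.

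**The case against.** The strongest reply is that the intent is plain. Section 11.3 is otherwise written for phase II, with time from random assignment and maintenance compared with observation. Sections 5.3.1 and 7.1.1 already make every treated patient evaluable for toxicity, phase I included. That stands: the fault is a conflict between 11.3 and those sections, and probably a drafting omission. It does not remove the need for a correction, because 11.3 is the only text that says which patients enter the safety summaries.

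It can also be said that an all-randomized set is one way to bring in an untreated observation arm. That is fair, and the fix keeps those patients. It does not justify counting never-dosed combination patients.

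A reader might infer three stronger things that the documents do not support.

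- *Phase I safety data are lost, particularly after the DLT window.* They are not. Appendix D schedules AE assessment at every treatment visit and at end of treatment, and 12.4 has the data and safety monitoring committee review toxicities every three months.
- *Pre-treatment SAEs left out under 8.3 never reach the nivolumab manufacturer.* This is not shown. Section 8.3 has sites report to the Sponsor-Investigator, who reports onward, but Appendix E may give a direct route, with its own contact details and a 24-hour limit. Only the difference between the texts is established.
- *The SAE follow-up periods, 90 days in 8.3 and 30 days in Appendix E, are a further contradiction.* These differ by recipient, and a cross-reference is enough.

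**Conclusion.** The safety population in 11.3 is wrong as written. It excludes 9 to 12 patients, 15-19% of those planned, whom objective 3.3.1 covers, and it includes combination-arm patients who are never dosed. Nothing is lost if it is corrected before analysis, so this is an inexpensive correction that should be made.

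The nonserious AE windows conflict by at least 70 days, and the visit schedule does not support the longer one. This part affects what is captured as well as how it is tabulated. The 63 to 77 days without contact rest on the assumption that termination coincides with the last dose.

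The pre-treatment SAE rules differ, and no loss of SAEs is demonstrated.

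Section 11.3 is also silent on assigned versus received treatment and on where events after cross-over belong, and no start point is given for AE collection in the observation arm. These are missing details, not contradictions. Sample size and power are unaffected throughout.

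**What to change.** In 11.3, define the safety population as all patients who receive at least one dose of either study drug in phase I or phase II, plus all patients randomized to observation. Analyse by treatment received, show phase I by dose level, and do not count events after cross-over under observation.

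Reconcile 8.1.1, 8.3 and Appendix E to one nonserious AE window, including whether new systemic therapy ends it, and to one pre-treatment SAE rule. Then make the follow-up schedule in 6.2, 6.3 and Appendix D match the window kept.

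The cost is wording. If the 100-day minimum is kept, it adds at least 70 days of nonserious AE collection per treated patient, which a phone contact could cover.
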